### 11.3 Analyses

Efficacy analyses:

There will be one primary pair-wise comparison of the efficacy endpoints: shortened duration therapy versus standard duration therapy. Comparisons will be simple, direct two-sample comparisons of randomised treatment groups unadjusted for baseline covariates. If there is evidence of substantial imbalance at baseline in important covariates, further adjusted analyses will also be performed. If any randomisation mistakes occur, such that patients incorrectly receive the wrong treatment, then key efficacy endpoints will be performed where these patients will be excluded.

The primary analysis will compare randomised treatment groups on an ITT basis including all available data. The primary endpoint, SVR12, will be calculated for each patient based on all available data. Treatment arms will be regarded as non-inferior if the difference in proportion between regimens has a lower limit greater than -12%. Secondary analyses will compare randomised treatment groups based on available data (per protocol).

Proportions and 95% confidence intervals will be reported for both the primary and secondary virological endpoints. These will be provided overall, by treatment duration, by HCV genotype and by HIV status, and will be assessed for both the ITT and PP populations.

SVR 4, SVR 12 and SVR 24 rates will be compared to SVR rates demonstrated in historical controls in the ATAHc I, ATAHc II, DARE-C I and DARE-C II studies. Differences in proportions between studies will be summarised as n (%) in each group, with percent difference between cohorts with 95% confidence interval.

Factors associated with ITT study population treatment efficacy will be evaluated by univariate analysis, and will include, but are not limited to, the following variables: socio-demographic factors (age, gender, ethnicity); virological factors (baseline HCV viral load, HCV genotype); risk behaviors (injecting drug use, sexual behaviour); and HIV co-infection.

Additional treatment efficacy evaluations will be conducted among the *per protocol study population*, defined as subjects who receive >80% of planned treatment.

The impact of 80/80 adherence, 90/90 adherence, 100/100 adherence, on-treatment adherence and early discontinuation on SVR will also be evaluated.

To assess HCV reinfection, among people with virological suppression, participants with HCV RNA recurrence (detectable HCV RNA following HCV virological suppression) will be identified. HCV RNA sequencing will be performed on the first available detectable HCV RNA sample and the first available detectable HCV RNA sample following HCV RNA recurrence. HCV reinfection will be defined by the detection of infection with an HCV strain which was distinct from the primary infecting strain based on previously defined genetic distance-based cut-offs for HCV reinfection and HCV viral relapse(72), patristic distance-based cut-offs and phylogenetic tree construction (86). Rates of HCV reinfection will be calculated using person-time of observation up to 48 months following the end of treatment. Modified intention-to-treat analyses will also be performed in which individuals with confirmed reinfection are removed from the efficacy analysis.

Immunological and virological assays will also be performed to assess the impact of HCV treatment on immune responses during treatment.

A final full statistical analysis plan will be written and signed off by the Protocol Steering Committee prior to final study data lock.

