#### **1.4 ATAH C I, ATAH C II, DARE-C I and DARE-C II studies**

The Australian Trial in Acute Hepatitis C (ATAHC) was an NIH funded multicentre prospective cohort study of the natural history, and outcomes following treatment with PEG (with or without RBV) in individuals with acute and early chronic HCV infection, with the final results published in *Gastroenterology* (60). Between 2004 and 2008, 167 subjects with acute and early chronic HCV infection were enrolled throughout Australia, of whom 111 (76%) subjects with detectable HCV RNA at screening elected to undertake treatment. 57% of the treated population were GT 1 and the median estimated duration of infection was 25 weeks, meaning that around half the patients had early chronic HCV infection. 33% of subjects were HIV co-infected. Final analysis of treatment outcomes in the 74 HCV mono-infected subjects who commenced treatment with PEG monotherapy demonstrated SVR rates of 55% and 72% by intention-to-treat and per-protocol analysis, respectively.

A second study (ATAHC II) was funded by the NIH for 5 years in 2010. One of the primary aims of this subsequent study is to explore potential therapeutic strategies aiming to enhance treatment efficacy and acceptability in the setting of recently acquired HCV infection (duration of infection <18 months). Within this second trial, a strategy of individualised response guided therapy was explored in which duration of therapy with PEG and RBV for acute and early chronic HCV infection was based on time to first undetectable HCV RNA, with total treatment duration ranging between 8-48 weeks. Eighty-two participants (HIV-positive 62%) were enrolled in ATAH C II (treated, n=52). SVR12 was 71% (37/52) with the majority (56%) receiving shortened therapy (8 or 16 weeks) with a combined SVR12 of 93% (unpublished data). SVR was associated with shorter treatment duration (OR 17.55; p=0.001) (unpublished data).

DARE-C I, a sub-study of ATAH C II, was established in 2013 to evaluate the safety and efficacy of response guided therapy with PEG, weight-based RBV and telaprevir (TVR) for recently acquired GT1 HCV infection (duration of infection 6-18 months). Treatment duration was dependent on time to first HCV RNA below the limit of detection and ranged between 8-24 weeks. Between April 2013 and May 2014, 14 participants

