(79% HIV-positive) were enrolled. SVR12 by ITT was 71% (10/14) (unpublished data). By treatment duration, SVR12 was 71% (5/7) in those receiving PEG/RBV/TVR for 8 weeks, 100% (3/3) in those receiving PEG/RBV/TVR for 12 weeks and 100% (2/2) in those receiving PEG/RBV/TVR for 12 weeks + PEG/RBV for 12 weeks (24 weeks) (unpublished data). In those with HIV, SVR12 was 73% (8/11) (unpublished data).

DARE-C II is an ongoing pilot study exploring the safety, efficacy and feasibility of the dual interferon-sparing combination of SOF plus RBV in participants with recent HCV infection (duration of infection <12 months). The study is closed to recruitment. Results will be presented at the American Association for the Society of Liver Disease (AASLD) meeting in November 2015.

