### 4.1 Summary of study design

This study will be conducted as a phase III randomised, open-label, non-inferiority multicentre international trial.

A total of 250 people with recently acquired hepatitis C will be enrolled and randomised.

The number of participants with HCV/HIV coinfection enrolled to the study will be capped at 70% (or less than 175 participants) of the total study population. In addition, the number of participants with HCV reinfection enrolled to the study will be capped at 20% (or less than 50 participants) of the total study population.

The study consists of a screening phase (-12 to -4 weeks), treatment commencement from baseline, randomisation between week 5 and 6, treatment for another 6 weeks for those randomised to standard therapy (12 weeks of treatment) or end of treatment for those randomised to shortened treatment (6 weeks of treatment). All participants will then enter the follow-up phase (96 weeks) to evaluate treatment response and reinfection (Figure 1). Randomisation will be using blocks and will be stratified by study site and HIV status.

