## **11 Statistics**

### **11.1 Sample size**

The primary objective of this trial is to establish the non-inferiority of short duration treatment (6 weeks) to the standard duration treatment (12 weeks).

Assuming an expected SVR of 90% in the control arm, 113 participants per arm will be required to give 80% chance that the two sided confidence interval of the difference between regimens has a lower limit greater than -12%.

A total of 250 subjects enrolled and randomised will comprise the intention-to-treat (ITT) population and will form the study population for evaluation of the primary and secondary endpoints.

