- To evaluate the immunological factors associated with treatment induced clearance and reinfection;
- To evaluate patient interest and attitudes towards long acting parenteral hepatitis C therapy (Long-Acting Hepatitis C Therapy Questionnaire).

Hypothesis

Six weeks treatment with sofosbuvir/velpatasvir is non-inferior to twelve weeks treatment with sofosbuvir/velpastavir as assessed by sustained virological response at 12 weeks post treatment in the intention-to-treat population (SVR12).

Study design (Figure 1)

This is an open label multicentre study. The study consists of a screening phase, treatment phase and follow-up phase to evaluate treatment response and reinfection. Participants will be required to wait a minimum of four weeks from screening before commencing treatment to assess for spontaneous clearance. The maximum wait period allowed between screening and baseline is 12 weeks.

[figure not shown]

Figure 1: Study Schema

Sample size and power

The primary objective of this trial is to establish the non-inferiority of short duration treatment (6 weeks) to the standard duration treatment (12 weeks). Assuming an expected SVR of 90% in the control arm, 113 participants per arm will be required to give 80% chance that the two-sided confidence interval of the difference between regimens has a lower limit greater than -12%.

A total of 250 subjects enrolled and randomised will comprise the intention-to-treat (ITT) population and will form the study population for evaluation of the primary and secondary endpoints.

TYPE OF ANALYSIS

This document describes the primary statistical analysis for REACT study in accordance with protocol version 5.0.

Data Safety and Monitoring Board (DSMB) Analysis

This study has a DSMB to review the progress and safety of the study. The DSMB conducted an interim safety and adherence analysis when the first 50 participants had either reached post-treatment week 12 or dropped out of the study and then when a further 10 per arm reached 12 weeks post treatment. At the second review the DSMB recommended termination of the short arm of the study due to inferiority. At the stage of the DSMB recommendation, a total of 196 participants had been randomised, 192 had completed their randomised treatment, a further 4 were randomised to receive 6 weeks and extended to 12 weeks. Therefore, the primary analysis population will be based on 192 participants (99 in standard Arm, and 93 in shortened arm).

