Primary analysis: Post-treatment week 12

The analysis for the primary endpoint, SVR12, will be conducted after all participants have completed the post-treatment week 12 visit or prematurely discontinued from study. All the safety and efficacy data through to the post-treatment week 12 visit will be cleaned, finalised, and included for the analysis.

GENERAL CONSIDERATIONS FOR DATA ANALYSES

Statistical Methods

Analysis results will be presented using descriptive statistics. For categorical variables, the number (n) and percentage of participants in each category will be presented. For continuous variables, the number of participants (n), mean and standard deviation (SD), median, interquartile range (IQR, Q1-Q3), range (minimum, maximum) will be reported; for inclusion in the manuscript, an appropriate determination will be made depending on the variable, size and distribution of the population studied.

Statistical tests will be 2-sided and performed at the 5% significance level unless specified.

For all efficacy endpoints, means and proportions with two-sided 95% confidence intervals (CI) will be determined. For the analysis of categorical outcomes, Chi-squared tests or exact equivalents (for small numbers) will be used. For comparison of continuous measures, t tests or non-parametric equivalents will be used as appropriate for the observed data distribution. Changes in injecting behaviour between screening, end of treatment and post-treatment week 12 will be compared using the McNemar test (exact binomial probability).

Analysis Sets

Analysis sets define the subjects to be included in an analysis. The number of participants eligible for each analysis set will be provided. Participants who were excluded from each analysis set will be summarised, with reasons for exclusion.

Full Analysis Set (ITT population)

The FAS includes all enrolled participants who were randomised. This will be the analysis set used for the primary efficacy and safety endpoints. Following the DSMB recommendation to cease the study, the primary analysis population will be based on 192 participants (99 in standard Arm, and 93 in shortened arm).

Modified Full Analysis Set

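### The historical SVR comparison in Protocol 11.3 names no REACT population; under the plan's ITT definition, losses before randomisation at week 5 to 6 leave the denominator on the REACT side only

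*Protocol*

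**What the plan says.** **Timing.** Protocol 4.1 describes "treatment commencement from baseline, randomisation between week 5 and 6". Every participant has therefore taken open-label drug for about five weeks before joining an arm.

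**REACT population.** Protocol 11.1 states that "A total of 250 subjects enrolled and randomised will comprise the intention-to-treat (ITT) population" and uses that population for the primary and secondary endpoints. The SAP, under Full Analysis Set, agrees: "The FAS includes all enrolled participants who were randomised".

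**Losses before randomisation.** Protocol 11.2 foresees them. It plans to describe these participants' baseline characteristics, adherence, risk behaviours and toxicity, but not their SVR.

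**Historical comparison.** Protocol 11.3 states that "SVR 4, SVR 12 and SVR 24 rates will be compared to SVR rates demonstrated in historical controls". It plans n (%) per cohort and a percent difference with a 95% interval. It names neither the REACT population nor the historical one.

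**Printed historical rates.**
- ATAHC I, mono-infected: 74 who commenced treatment, 55% by ITT (Protocol 1.4).
- ATAHC I, HIV co-infected: 35 who commenced, 74% by ITT (Protocol 1.3.3).
- ATAHC II: 37 of 52 treated (Protocol 1.4).
- DARE-C I: 10 of 14 enrolled, by ITT (Protocol 1.4).
- DARE-C II: no rate or denominator (Protocol 1.4).

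**The concern.** A difference between cohorts is interpretable only if both sides start counting at the same point. A participant who started drug and was lost at week 2 would be a failure in the historical rates above. In REACT the same participant would be in no SVR denominator. If the ITT population is used, part of any REACT advantage comes from having selected people who stayed on treatment until week 5 to 6. The confidence interval reflects sampling error only, so it would not show this.

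What is at stake is how a reader interprets SVR4, SVR12 and SVR24 against the earlier studies. The trial's main question is not at stake.

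**Working it through.** **1. Printed rates.** ATAHC II: 37/52 = 71.2%. DARE-C I: 10/14 = 71.4%. Both match the printed 71%. Both use the full treated or enrolled group as denominator.

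**2. Formula.** Let d be the share of starters lost before randomisation, p the SVR among those randomised, and s the SVR among those lost.

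- SVR from first dose = (1 − d) × p + d × s
- Overstatement = p − [(1 − d) × p + d × s] = d × (p − s)

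This is above zero whenever those lost clear virus less often than those randomised.

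**3. Inputs.** p = 90% is the control-arm assumption in Protocol 11.1. The documents give neither d nor s. I assume d = 2%, 5% or 10%. For s, I take 0 (every loss a failure, in line with the SAP's rule for loss to follow-up) and 50% (half of those lost clear virus).

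| d | SVR from first dose, s = 0 | Overstatement (points) | SVR from first dose, s = 50% | Overstatement (points) |
|---|---|---|---|---|
| 2% | 0.98 × 90 = 88.2% | 1.8 | 88.2 + 1.0 = 89.2% | 0.8 |
| 5% | 0.95 × 90 = 85.5% | 4.5 | 85.5 + 2.5 = 88.0% | 2.0 |
| 10% | 0.90 × 90 = 81.0% | 9.0 | 81.0 + 5.0 = 86.0% | 4.0 |

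**4. Effect on the planned interval, ATAHC II as example.** Assume 250 randomised with 225 responders (90%), s = 0, starters = 250/(1 − d) rounded to a whole number, and Newcombe intervals (the protocol names no method).

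| d | REACT | Difference from 37/52 (points) | 95% CI |
|---|---|---|---|
| 0 | 225/250 = 90.0% | 18.8 | 7.5 to 32.6 |
| 2% | 225/255 = 88.2% | 17.1 | 5.6 to 30.9 |
| 5% | 225/263 = 85.6% | 14.4 | 2.9 to 28.3 |
| 10% | 225/278 = 80.9% | 9.8 | −1.9 to 23.8 |

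Only at the top of the assumed range, with every loss a failure, does the interval reach zero. With s = 50% and d = 10%, the difference is 86.0 − 71.2 = 14.8 points.

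**5. What the earlier studies show.** The DARE-C I results by duration sum to 5/7 + 3/3 + 2/2 = 10/12 = 83.3%, against 10/14 = 71.4% by ITT. ATAHC I mono-infected rates were 55% by ITT and 72% per protocol. These gaps show that a rate can be sensitive to its denominator. The ATAHC I co-infected rates, 74% and 75% (Protocol 1.3.3), show that it need not be.

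**The case against.** **The population is inferred.** Section 11.3 does not say that the comparison is ITT against ITT. The same section also reports virological endpoints per protocol, and the SAP describes ETR and SVR4 as proportions of treated participants. A reader might take the mismatch as stated policy; it is not. It follows if the plan's default population is used. The objection leaves the omission standing, because none of the ITT, modified ITT or per-protocol definitions provides for losses before randomisation.

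**The earlier gaps do not measure run-in loss.** A reader might take the 12-point DARE-C I gap or the 17-point ATAHC I gap as the size of the problem. The protocol does not say why two DARE-C I participants fall outside the duration groups. The ATAHC I gap reflects a whole peginterferon course, in which 77% received at least 80% of treatment (Protocol 1.3.2). Neither is specific to the first five or six weeks, and both regimens were interferon-based. Nor do the documents support saying that drop-out separates ITT from per-protocol rates in both target groups: the co-infected gap was one point, and co-infected participants may make up to 70% of REACT. This objection stands in full.

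**Counting every loss as a failure is an extreme case.** Protocol 4.3 asks that participants who stop drug be followed wherever possible, so some will have an observed result. This stands, and is why the s = 50% column is shown.

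**The analysis is minor.** It is descriptive, with no margin or decision rule, and does not appear in the SAP. The controls also differ in regimen and infection duration (under 18 months in ATAHC II and 6 to 18 months in DARE-C I, against 12 months or less here). This limits the weight of the point. However, regimen is the contrast of interest, while the denominator difference is an avoidable artefact.

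**Conclusion.** The point holds as a modest improvement to a secondary, descriptive analysis. Section 11.3 leaves the REACT population unstated. Applying the plan's own ITT definition gives a comparison that favours REACT whenever those lost in the first weeks clear virus less often than those randomised. The mismatch can be shown for three of the four historical studies; DARE-C II has no printed rate.

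The size is unknown because the documents give neither the share lost nor those participants' SVR. With 90% among those randomised and 2% to 10% lost, the overstatement is 1.8 to 9.0 points if none of those lost clear virus, and 0.8 to 4.0 points if half do. The upper figure should not be read as an estimate.

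A reader might also infer that the run-in biases the primary result. It does not on this ground: both arms pass through the same weeks before allocation, so the randomised comparison of 6 with 12 weeks is unaffected.

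**What to change.** In Protocol 11.3, and in the SAP if the comparison is kept:

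- Define the REACT denominator for historical comparisons as all participants who took at least one dose.
- For those who withdrew before randomisation, use observed SVR where follow-up under Protocol 4.3 provides it, count the rest as failures, and report how many there were.
- For an arm-specific historical comparison, use r × (arm SVR) + (1 − r) × (SVR among pre-randomisation withdrawals, missing = failure), where r is the fraction of starters who were randomised. Give a bootstrap or delta-method interval.
- Keep the randomised population for the comparison of 6 with 12 weeks.

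The cost is a few sentences and a little more analysis, with no change to sample size or procedures. Protocol 11.2 already commits to evaluating these participants, but HCV RNA outcome is not on its list and would need to be added. The REACT rates in the historical comparison would probably be slightly lower.

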## **12 Data Safety and Monitoring Board (DSMB)**

A data safety and monitoring board (DSMB) will consist of at least 1 statistician and 2 practicing gastroenterologist/infectious diseases specialists. All DSMB members will be independent of the study and the Kirby Institute. The meeting will include the interim efficacy and safety analysis which will be performed when the first 50 subjects in each arm have either received treatment and completed 12 weeks of follow-up post treatment (SVR12) or dropped out of the study. Additional DSMB meetings will be scheduled at a frequency commensurate with the risk as determined by the DSMB.

The Principal Investigator and the institution where the study will be conducted will permit study-related monitoring, audits, ethics committee review and regulatory inspection providing direct access to source documents.

Data will be collected on study specific electronic or paper copy case record forms. The Principal Investigator is responsible for ensuring the data collected are complete, accurate and recorded in a timely manner.

## **13 Data collection, source documents and record retention**

### **13.1 Submission of data**

Electronic CRFs: following each participant visit the designated site staff will complete the visit specific eCRF. Once all required information is received the eCRF shall be considered complete. Project Team staff will then monitor the data for completeness and accuracy. Any eCRF discrepancies, either manual or automatic, will be addressed with the site staff for clarification.

The site Principal Investigator is responsible for ensuring the completion of accurate source documentation to support data collected on case report forms. Source documents include all recordings of observations or notations of clinical activities and all reports and records necessary for the evaluation and reconstruction of the trial. Source documents include, but are not limited to; participant medical records, laboratory reports, ECG tracings, X-rays, radiologist reports, participant diaries, biopsy reports, ultrasound images, participant progress notes, pharmacy records and any other reports or records of procedures performed in accordance with the protocol.

It is not acceptable for the CRF to be the only record of study participation and progress must also be recorded in the each person's medical record. This is to ensure that anyone accessing the medical record has adequate knowledge that the person is a clinical trial participant.

Any document that acts as a source document (the point of the initial recording of a piece of data) should be signed and dated by the person recording or reviewing the data for issues of medical significance (for example the review of laboratory reports). Persons signing the source documents must be listed as a site staff member.

The sponsor's monitor will visit sites to conduct source document verification. The number of visits will depend upon study complexity and recruitment rate; however, the monitor will conduct a minimum of two source data verification visits during the study. These should occur shortly after enrolment of the first participant(s) and following completion of all study visits.

The Principal Investigator is responsible for retaining all essential documents listed in ICH Good Clinical Practice guidelines. These must be organised in a comprehensive filing system that is accessible to study monitors and other relevant personnel.

